8.2. Baseline Characteristics and Subject Disposition

Overall Baseline and demographic data will be summarized using descriptive statistics. Subject disposition (e.g., the number of Subjects enrolled, completed, and discontinued) will be summarized and medical history data will be listed.

8.3. Endpoint Analyses

Full descriptions of statistical assessments for primary and secondary endpoints are given in a separate statistical analysis plan. Included herein are brief descriptions.

8.3.1. Primary Endpoint

The primary endpoint analysis will compare the difference in the overall and heart failure related healthcare costs between subjects treated with the Furoscix Infusor 30 days post discharge from the emergency department for worsening heart failure due to fluid overload with propensity score matched controls treated in the hospital for \leq 72 hours through 30 days post discharge. Propensity scoring methods will be described in the statistical analysis plan. Comparison of these data between the matched (paired) cohorts will be conducted via a t-test or a Wilcoxon signed-rank test depending on distribution of data.

8.3.2. Secondary Endpoints

Outcomes for the endpoints related to healthcare resource utilization (i.e., Secondary Endpoints 1-4) will be evaluated by appropriate statistical test dependent on the distribution of the outcome. Health-related quality of life outcomes will be evaluated for the Furoscix cohort only and will descriptively compare KCCQ-12 questionnaire responses at Day 0 versus Day 30. Change in BNP or NT-proBNP will be evaluated for the Furoscix cohort only and will descriptively compare values obtained at Day 0 versus Day 30. Subject and/or caregiver satisfaction with Furoscix Infusor will be descriptive.

8.4. Safety Analyses

There are no pre-planned analyses to compare Furoscix versus hospitalized cohort on the basis of safety. However, the safety of Furoscix will be monitored during the trial, and identified safety issues (including AEs, SAEs, and adverse reactions) will be summarized descriptively for the Furoscix cohort.

The incidence (number and percentage of subjects) of adverse events will be presented overall and by MedDRA System Organ Class and Preferred Term for the Furoscix cohort. Reactions at the infusion site and frequency of these reactions will be reported. This analysis will be repeated for serious adverse events, for treatment-related adverse events, and for adverse events leading to premature study withdrawal.

9. RESPONSIBILITIES

9.1. Investigator Responsibilities

9.1.1. Good Clinical Practice

The Investigator will ensure that this study is conducted in full compliance with the principles of the “Declaration of Helsinki” (as amended in Edinburgh, Tokyo, Venice, Hong Kong, and South Africa), International Council for Harmonization of Technical Requirements for Pharmaceuticals for Human Use guidelines, or with the laws and regulations of the country in which the research is conducted, whichever affords the greater protection to the study Subject. For studies conducted under a United States investigational new drug application, the Investigator will ensure that the basic principles of “Good Clinical Practice,” as outlined in 21 CFR 312, subpart D, “Responsibilities of Sponsors and Investigators,” 21 CFR, part 50, 1998, and 21 CFR, part 56, 1998, are adhered to. This study is also subject to and will be conducted in compliance with 21 CFR, part 320, 1993, “Retention of Bioavailability and Bioequivalence Testing Samples.”

9.1.2. Institutional Review Board and Independent Ethics Committee Approval

This protocol and any accompanying material to be provided to the Subject (such as advertisements, Subject information sheets, or descriptions of the study used to obtain informed consent) will be submitted, by the Investigator, to an institutional review board or independent ethics committee. Approval from these bodies must be obtained before starting the study and should be documented in a letter to the Investigator specifying the protocol number, protocol version, documents reviewed, and date on which the committee met and granted the approval.

Any modifications or amendment to the protocol will be submitted to these bodies for approval prior to implementation.

9.1.3. Informed Consent

It is the responsibility of the Investigator or designee to obtain written informed consent from each individual participating in this study after adequate explanation of the aims, methods, objectives, and potential hazards of the study and prior to undertaking any study-related procedures. The Investigator or designee must utilize a consent form approved by the institutional review board for documenting written informed consent. Each completed informed consent will be appropriately signed and dated by the Subject and the person obtaining consent. A copy of the signed consent form will be provided to the Subject.

9.1.4. Confidentiality

All information about the nature of the proposed investigation provided by the Sponsor or study monitor to the Principal Investigator (with the exception of information required by law or regulations to be disclosed to the institutional review board, the Subject, or the appropriate regulatory authority) must be kept in confidence by the Principal Investigator.

The Investigator will assure that Subjects’ anonymity will be strictly maintained and that their identities are protected from unauthorized parties. Only Subject initials and an identification code (i.e., not names) should be recorded on any form submitted to the Sponsor and institutional review board. The Investigator must keep a Subject log showing codes and, names, for all enrolled in the trial.

9.1.5. Compensation, Insurance, and Indemnity

Information regarding compensation, insurance, and indemnity is addressed in the Clinical Trial Research Agreement.

9.1.6. Study Files and Retention of Records

The Investigator will maintain adequate and accurate records to enable the conduct of the study to be fully documented and the study data to be subsequently verified. These documents should be classified into 2 separate categories including (although not limited to) the following: (1) Investigator's study file, and (2) Subject clinical source documents.

The Investigator's study file will contain the protocol/amendments, CRF and query forms, approval by the institutional review board with correspondence, informed consent, drug records, staff curriculum vitae and authorization forms, and other appropriate documents and correspondence.

Subject clinical source documents would include (although is not limited to) the following: Subject hospital/clinic records, physician's and nurse's notes, appointment book, original laboratory reports, electrocardiogram, x-ray, pathology and special assessment reports, consultant letters, screening and enrollment log, etc.

All clinical study documents must be retained by the Investigator until at least two years after the last approval of a marketing application in an International Conference on Harmonization region (i.e., United States, Europe, or Japan) and until there are no pending or contemplated marketing applications in the region(s); or, until two years after the investigational new drug is discontinued and regulatory authorities have been notified. The Investigator must notify scPharmaceuticals prior to destroying any clinical study records.

Should the Investigator wish to move study records to another location, arrangements must be made to store these in sealed containers so that they can be returned sealed to the Investigator in case of a regulatory audit. Where source documents are required for the continued care of the Subject, appropriate copies should be made for storage outside of the site.

9.1.7. Case Report Forms

For each subject who signs informed consent, a CRF must be completed and signed by the principal Investigator or sub-Investigator within a reasonable time period after data collection. This also applies to records for those Subjects who fail to complete the study. If a Subject withdraws from the study, the reason must be noted on the CRF. If a Subject is withdrawn from the study because of a treatment-limiting AE, thorough efforts should be made to clearly document the outcome.

9.1.8. Protocol Deviations

If a situation requires a deviation from the Clinical Study Protocol, the Principal Investigator or other investigator in attendance will contact the Medical Monitor as soon as possible in order to discuss the situation and agree on an appropriate course of action. If possible, the Principal Investigator or designee will contact the Medical Monitor prior to making the deviation. Any departure from the Clinical Study Protocol together with the rationale for the deviation must be recorded on the CRF and source document.

9.1.9. Disclosure of Data

The Principal Investigator agrees by his/her participation that the results of this study may be used for submission to national and/or international registration and supervising authorities. If required, these authorities will be provided with the name of the Principal Investigator, their addresses, qualifications and extent of involvement. It is understood that the Principal Investigator is required to provide scPharmaceuticals with all study data, complete reports, and access to all study records.

Data generated by this study must be available for inspection by the Food and Drug Administration, by scPharmaceuticals and its designees, and the institutional review board as appropriate. At a Subject's request, medical information may be given to his or her personal physician or other appropriate medical personnel responsible for his or her welfare. Subject medical information obtained during the course of this study is confidential and disclosure to third parties other than those noted above is prohibited.

9.1.10. Financial Disclosure

The United States Food and Drug Administration Financial Disclosure by Clinical Investigators (21 CFR 54) regulations require Sponsors to obtain certain financial information from Investigators participating in covered clinical studies; each Principal Investigator and Sub-investigator is required to provide the required financial information and to promptly update scPharmaceuticals with any relevant changes to their financial information throughout the course of the clinical study and for up to 1 year after its completion. This rule applies to all Principal Investigators and Sub-investigators participating in covered clinical studies to be submitted to the Food and Drug Administration in support of an application for market approval.

9.1.11. Drug and Device Product Accountability

The Investigator or designee is responsible for ensuring adequate accountability of all used and unused study product. This includes acknowledgment of receipt of each shipment of study product (quantity and condition) and Subject dispensing records and returned study product. Dispensing records will document quantities received and quantities dispensed to Subjects, including lot number, date dispensed, Subject identifier number, Subject initials, and the initials of the person dispensing the medication.

At the end of the study, following final product reconciliation by the monitor, the study site will be instructed by the Sponsor to return all unused study product supplies.

9.1.12. Inspections

The Investigator will provide access to source documents and all study records for this trial to appropriately qualified personnel from scPharmaceuticals or its representatives, and to regulatory authority inspectors.

9.2. Sponsor Responsibilities

9.2.1. Study Materials and Instructions

It is the Sponsor's responsibility to ensure that the Investigator is provided with the documents and other study materials necessary to conduct the study. Examples of those materials include, but are not limited to: protocol, Investigator's Brochure, study product, CRF, logs, etc. The Sponsor will also provide training and oversight through site and medical monitoring.

9.2.2. Protocol Modifications

Protocol modifications, except those intended to reduce immediate risk to study Subjects, will be made by Sponsor-initiated amendment. Approval from an institutional review board must be obtained before changes can be implemented.

Note that this provision does not apply to early stopping or sample size increases that are governed by the adaptive nature of the clinical trial design.

9.3. Joint Investigator and Sponsor Responsibilities

9.3.1. Access to Information for Monitoring

In accordance with International Conference on Harmonization Good Clinical Practice guidelines, the study monitor must have direct access to the Investigator's source documentation in order to verify the data recorded in the CRF for consistency.

The monitor is responsible for routine review of the CRF at regular intervals throughout the study, to verify adherence to the protocol, and the completeness, consistency and accuracy of the data being entered. The monitor should have access to any Subject records needed to verify the entries on the CRF. The Investigator agrees to cooperate with the monitor to ensure that any problems detected in the course of these monitoring visits are resolved.

9.3.2. Study Discontinuation

Both the Sponsor and the Investigator reserve the right to terminate the study at any time. Should this be necessary, both parties will arrange discontinuation procedures and notify the appropriate regulatory authorities and institutional review board(s). In terminating the study, the Sponsor and the Investigator will assure that adequate consideration is given to the protection of the Subjects' interests.

Note that this provision does not apply to early stopping or sample size increases that are governed by the adaptive nature of the clinical trial design.

1. ADMINISTRATIVE INFORMATION

This SAP will be revised as necessary. The statistical analysis lead will be responsible for any revisions and obtaining appropriate approvals. The trial statistician will be responsible for execution of this SAP and distribution of revisions to the appropriate clinical staff.

2. BACKGROUND

Heart failure (HF) affects 6.5 million adults in the United States, a figure that is expected to grow to 8 million by 2030. In the United States, HF is implicated as the cause of at least 1-2 million hospitalizations and 700,000 emergency department (ED) visits annually, and HF admissions generate the highest number of 30-day readmissions among Medicare enrollees. It is also estimated that 90% of patients presenting to the ED with worsening HF are admitted to the hospital and approximately 50% of hospital admissions for HF admitted from the emergency department could potentially be avoided.

Intravenous furosemide is commonly indicated for the management of edema which is commonly present in worsening HF as the absolute bioavailability of oral furosemide is low, highly variable and is exacerbated during an acute event. Recognizing this limitation of oral furosemide, national and international guidelines recommend that patients should be administered intravenous diuretics when significant signs and symptoms of volume overload are present. Thus, hospital admission or utilization of an observational unit is generally required. Admitting patients to the hospital, solely for the administration of intravenous furosemide, is expensive and increases risks of hospital-associated morbidity and mortality. Alternative treatment paradigms that shift HF management outside of the hospital are needed.

Approximately 60% of hospital admissions in patients with HF are due to sodium retention and volume overload. While subcutaneous administration of furosemide would enable diuresis as an outpatient, avoiding a hospital admission, the current commercially available furosemide injectable products have an alkaline pH and poor solubility making them unsuitable for subcutaneous administration. A novel, pH neutral formulation of subcutaneous furosemide (Furoscix, Furosemide Injection 80 mg/10 mL for subcutaneous use) has been developed to minimize burning and discomfort with subcutaneous administration and is delivered via the Furoscix Infusor: a wearable, pre-programmed on-body subcutaneous delivery system.

Furoscix administered 80 mg subcutaneously via the Furoscix Infusor, with 30 mg administered over the first hour followed by 12.5 mg per hour over the subsequent four hours produced similar exposures of furosemide and equivalent diuresis and natriuresis compared to two bolus injections of furosemide 40 mg dosed over 2 minutes, two hours apart.

The purpose of this study is to evaluate the economic impact of hospital avoidance and safety with management of worsening HF due to congestion with Furoscix administered via the Furoscix Infusor outside the hospital setting in patients initially presenting to the emergency department.

2.1. Schedule of Assessments

	DAY 0	DAY 1 (Phone)	DAY 2 - DAY 4 (Clinic)	DAY 7 (Phone)	DAY 14 - Day 21 (Phone)	Unscheduled (Clinic)	Unscheduled (Phone) ⁵	DAY 30 ±3 (Clinic)
Informed Consent	X							
Confirmation of Eligibility	X							
Medical History & Demographics	X							
Interim Medical History			X			X		X
Concomitant Medications	X	X	X	X	X	X	X	
Cardiopulmonary Exam ¹ , NYHA	X		X			X		X
Vital Signs ² , Height, Weight	X		X			X		X
Clinical Chemistries ³	X		X			X		X
Hematology	X		X			X		X
Urine Pregnancy Test	X							
KCCQ-12 Short Form	X							X
Device/Product Training	X							
Device/Product Administration ⁴	X	X						
Subject Diary		X	X	X	X	X	X	X
Comfort of Wear Questionnaire			X					
Skin Assessment	X		X					X
Adverse Events	X	X	X	X	X	X	X	X
Schedule Next Study Visit	X		X					
Phone Call Visit		X		X	X			
Suggested Telephone Script		X		X	X		X	

¹ Cardiopulmonary Exam includes consists of assessments of the following: jugular venous distension, lungs/chest, heart, abdomen and edema. Includes NYHA classification.

² Vital signs include respiratory rate, blood pressure, heart rate, and weight. BP and HR obtained after Subject resting in sitting position for 5 minutes. Height recorded Day 0 only.

³ Clinical Labs are done locally and include Cr, BUN, Na⁺, K⁺, Chl, CO₂, and Mg; BNP or NT-proBNP will be drawn and sent to a local laboratory

⁴ If Subject receives IV furosemide in the emergency department, the at-home treatment using Furoscix Infusor may begin one day later (i.e. not on Day 0). Subjects should be transitioned back to their oral maintenance diuretic regimen when clinically indicated at the discretion of the investigator (approximately 4 doses). After Subjects have been transitioned to their oral maintenance diuretic regimen, additional doses of Furoscix can be prescribed during the 30-day study period as needed based on the presence of clinical triggers (dyspnea on exertion, edema, and/or excess weight gain) as determined by the investigator. No more than 7 doses of Furoscix is permitted during the 30-day study period. Additional doses beyond 7 requires approval by the medical monitor. In addition to the scheduled phone and clinic visits, the investigator can utilize unscheduled clinic or phone visits for additional assessments at any time.

⁵ If Subject receives unscheduled at-home phone call by an HF nurse, or designee, the nurse, or designee, should perform assessments in Unscheduled (Phone) column.

3. DESCRIPTION OF ANALYSIS

The primary outcome will be assessed with a superiority testing framework on the basis of the following primary endpoint:

- a. Overall and heart failure related healthcare costs between subjects treated with the Furoscix Infusor 30 days post discharge from the emergency department for worsening heart failure due to fluid overload compared to propensity matched controls treated in the hospital for \leq 72 hours through 30 days post discharge.

3.1. Statistical Software

Analysis will be conducted in SAS version 9.4 or newer (SAS Institute, Cary, North Carolina, USA).

3.2. Baseline Variables

Baseline demographic and background clinical variables common to both the prospective cohort and the propensity-matched historical control group will be summarized. Additional variables applicable only to the prospective cohort will separately be summarized. Continuous variables will be summarized with means, standard deviations, medians, interquartile ranges, minima, and maxima. Categorical variables will be summarized with frequencies and percentages.

3.3. Important Considerations

3.3.1. Defined Populations applicable to the prospective arm

3.3.1.1. Intent to Treat (ITT) Population – Subjects who meet all of the inclusion criteria and none of the exclusion criteria and whose IRB-approved informed consent form has been signed and dated by all required parties.

3.3.1.2. Safety Population (SP) – Subset of the ITT received a dose of FUROSCIX (whether they completed or did not complete all study phases through 30-day follow up).

3.3.1.3. Evaluable Population (EP) – Subset of the SP who completed all the study phases as per the protocol.

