- e. agree to ensure that all associates, colleagues, and employees assisting in the conduct of the study(ies) are informed about their obligations in meeting the above commitments.
- f. agree to maintain adequate and accurate records in accordance with 21 CFR 312.62 and to make those records available for inspection in accordance with 21 CFR 312.68.
- g. will ensure that an IRB that complies with the requirements of 21 CFR Part 56 will be responsible for the initial and continuing review and approval of the clinical investigation. I also agree to promptly report to the IRB all changes in the research activity and all unanticipated problems involving risks to human subjects or others. Additionally, I will not make any changes in the research without IRB approval, except where necessary to eliminate apparent immediate hazards to human subjects.
- h. agree to comply with all other requirements regarding the obligations of clinical investigators and all other pertinent requirements in 21 CFR Part 312.

Investigator's Signature

Date

Print Name

ABBREVIATIONS

AE	adverse event
CRF	case report form
ED	emergency department
HF	heart failure
IFU	instructions for use
IV	intravenous
KCCQ	Kansas City Cardiomyopathy Questionnaire
NYHA	New York Heart Association
SAE	serious adverse event
TAU	treatment as usual
USA	United States of America

SYNOPSIS

SHORT TITLE	FREEDOM-HF
PROTOCOL TITLE	Economic Impact of Reducing Hospital Admissions for Patients Presenting to the Emergency Department with Worsening Heart Failure: An Adaptive Clinical Trial of Furoscix Infusor
PROTOCOL NUMBER	scP-01-005
SPONSOR	scPharmaceuticals, Inc.
INVESTIGATIONAL PRODUCT	Furoscix On-body Infusor drug-device combination product (hereinafter referred to as Furoscix Infusor)
STUDY OBJECTIVES	
1. To evaluate differences in healthcare resource utilization costs for subjects treated with the Furoscix Infusor outside the hospital ("Furoscix arm", "Furoscix cohort" or "Furoscix Infusor cohort") compared to patients receiving intravenous furosemide for ≤ 72 hours in the hospital setting for 30 days post-discharge from the emergency department.2. To evaluate the safety of Furoscix administered outside the hospital.3. To evaluate and describe quality of life and patient satisfaction for patients who receive the Furoscix Infusor outside the hospital setting.

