7.10.4. Documenting Adverse Events and Serious Adverse Events

All AEs, including SAEs that occur after dosing of study product must be documented in the Subject's medical records and on the CRF. The Investigator should attempt to establish a diagnosis of the event based on signs,

symptoms, and/or other clinical information. In such cases, the diagnosis should be documented as the AE and/or SAE term.

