3.4. Safety Objective

The safety analysis includes assessment of adverse events (AEs) and device performance. The safety of Furoscix will be monitored during the trial, and identified safety issues (including AEs, SAEs, and adverse reactions) will be summarized descriptively in the safety population for the Furoscix cohort.

The incidence (number and percentage of subjects) of adverse events will be presented overall and by MedDRA System Organ Class and Preferred Term for the Furoscix cohort. Reactions at the infusion site and frequency of these reactions will be reported. This analysis will be repeated for serious adverse events, for treatment-related adverse events, and for adverse events leading to premature study withdrawal.

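### Read literally, the SAP's Safety Population leaves out a dosed subject who breached an entry criterion, which does not match the protocol's safety cohort or SAP 3.3.4

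*SAP*

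**What the plan says.** **SAP definitions.** Section 3.3.1.1 defines ITT as "Subjects who meet all of the inclusion criteria and none of the exclusion criteria and whose IRB-approved informed consent form has been signed", with dates, by everyone who has to sign it. It does not say that eligibility is taken as judged at enrolment. Section 3.3.1.2 makes the Safety Population a "Subset of the ITT received a dose of FUROSCIX". Section 3.3.1.3 nests the Evaluable Population inside the Safety Population.

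**SAP use of the sets.** Section 3.4 says that safety issues, including AEs, SAEs and adverse reactions, "will be summarized descriptively in the safety population for the Furoscix cohort". Its next paragraph says that AE incidence "will be presented overall and by MedDRA System Organ Class and Preferred Term for the Furoscix cohort", and it repeats that table for SAEs, treatment-related events and events leading to withdrawal. Section 3.3.4 describes the Evaluable Population by enrolment, receipt of drug and completion of the study phases. It attaches the ITT label to people who were enrolled but not dosed, and it plans a separate summary for them. No section plans a summary for people who were dosed but ineligible.

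**Protocol.** Section 8.4 says that safety issues "will be summarized descriptively for the Furoscix cohort". The first objective in the synopsis attaches that cohort label to its comparison "for subjects treated with the Furoscix Infusor outside the hospital". Section 7.10.4 states: "All AEs, including SAEs that occur after dosing of study product must be documented". None of these carries an eligibility condition.

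**The concern.** A safety set is normally defined by exposure alone. Here it inherits an eligibility condition, and a consent-form condition, from its parent set. A dosed subject later found to fail a limit on renal function, vital signs or background diuretic dose would be outside ITT. That subject would therefore be outside the Safety Population and the summary tied to it. The same applies to a dosed subject whose consent form lacks a required signature or date.

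Safety outside the hospital is the protocol's second objective, and no safety comparison with the hospitalised controls is planned. The single-arm description of the Furoscix cohort is therefore the whole safety analysis, and its denominator should not be in doubt.

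The situation can arise. Protocol 6.2 allows screening, enrolment and first dose on one day. Protocol 6.2.1 lets usual-care tests done within 12 hours of enrolment serve as study data. Neither passage shows how often a deviation would come to light later.

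**Working it through.** **1. The plan's own figure.** The nearest computable number is the sample size in SAP 3.5.2. Inputs are a difference of 8,600 − 6,500 = $2,100, a standard deviation of $3,045, two-sided alpha 0.05 and power 80%.

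n per group = 2 × (1.960 + 0.842)² × (3,045 / 2,100)² = 2 × 7.849 × 2.1025 = 33.0 (33.005 before rounding), which rounds up to 34, or 68 in total.

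The plan's figure reproduces. It matters here only because it sets the denominator.

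**2. Set logic.** Take a subject who was dosed and breached one criterion.

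| Text | Condition for inclusion | Subject included? |
|---|---|---|
| SAP 3.3.1.1, ITT | every criterion met, consent complete | No |
| SAP 3.3.1.2, Safety Population | in ITT and dosed | No |
| SAP 3.4, first paragraph | in the Safety Population | No |
| SAP 3.4, incidence tables | Furoscix cohort, not defined as an analysis set | Unclear |
| SAP 3.3.4 | enrolled and dosed (and completed, for the evaluable set) | Not barred by eligibility |
| Protocol 8.4 with the synopsis | treated with the Infusor | Yes |
| Protocol 7.10.4 | event after dosing (recording rule) | Recorded |

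The exclusion follows from the first three rows. The rest show that it is not applied consistently.

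**3. Effect on a reported rate.** Let N subjects be dosed, x of them have an event, and k be left out, of whom e had an event. The full rate is x/N and the reported rate is (x − e)/(N − k). The reported rate is lower when e/k > x/N and higher when e/k < x/N.

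With N = 34, one subject is 1/34 = 2.9% of the denominator. Illustration with an assumed x = 5, so that the full rate is 5/34 = 14.7%:

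| k left out | all k had an event | none did |
|---|---|---|
| 1 | 4/33 = 12.1% | 5/33 = 15.2% |
| 2 | 3/32 = 9.4% | 5/32 = 15.6% |
| 3 | 2/31 = 6.5% | 5/31 = 16.1% |

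At N = 75, the size that the plan does not expect to exceed, with an assumed x = 11, the full rate is 11/75 = 14.7%. Leaving out one subject gives 10/74 = 13.5% or 11/74 = 14.9%.

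**4. Chance that it happens at all.** If a share r of dosed subjects is later found ineligible, independently of one another, the chance of at least one is 1 − (1 − r)^N. The documents give no r, so the range is assumed.

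| r | N = 34 | N = 75 |
|---|---|---|
| 1% | 29% | 53% |
| 2% | 50% | 78% |
| 5% | 83% | 98% |
| 10% | 97% | over 99% |

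**The case against.** The best reply is that ITT here simply means enrolled. The protocol allows enrolment only of subjects who satisfy the criteria, eligibility is confirmed on Day 0, and the SAP's ITT wording follows that rule. SAP 3.3.4 uses the label for enrolled subjects and describes its analysis set by enrolment and dosing. Nothing in either document describes reassessing eligibility later and removing people. This stands as a plausible account of intent. It does not settle the text: 3.3.1.1 conditions on "Subjects who meet all of the inclusion criteria and none of the exclusion criteria", and a programmer following it would drop a confirmed violator.

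Three stronger readings are tempting, and the documents do not support them.

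- A reader might infer that such a subject disappears from every AE table. Only the first paragraph of SAP 3.4 names the Safety Population. The incidence tables and their repeats name the Furoscix cohort, which on the protocol's description would include the subject. Loss from all tables is one reading. The other leaves two denominators in adjacent paragraphs.
- A reader might infer that reported rates are biased downward. That needs the excluded subjects to have more events than the rest. Some criteria, such as renal function, make this plausible. Others, such as taking part in another study, have no obvious link to harm. The first table of rates above moves both ways.
- A reader might take the creatinine-clearance equation as evidence that entry errors are likely, since the factor for women appears in the synopsis and not in section 4.2. That may be a loss in text extraction, and it carries no weight here.

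It is also true that no data are lost. Events after dosing are recorded, SAEs go to the sponsor within 24 hours, and protocol deviations are recorded on the CRF.

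**Conclusion.** The defect holds as a fault in the definition. The literal SAP text leaves a dosed but ineligible subject out of the summary tied to the Safety Population. That does not match protocol 8.4, is narrower than what protocol 7.10.4 has recorded, and sits awkwardly with SAP 3.3.4.

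Its practical size is unknown. Each subject is about 3% of a denominator of 34, and whether any would be affected depends on an ineligibility rate that the documents do not give. The event counts and rates used above are assumptions that show scale, not forecasts. Bias in a particular direction, and loss from all safety tables, are not established.

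This should be fixed before the safety tables are programmed. It does not affect the sample size, the collection of safety data or the reporting of SAEs.

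**What to change.** - **SAP 3.3.1.2:** define the Safety Population as every subject who received any amount of Furoscix, regardless of eligibility or consent-form deviations, and not as a subset of ITT.
- **SAP 3.3.1.1:** define ITT as all consented and enrolled subjects, in line with how 3.3.4 uses the term.
- **SAP 3.4:** name the Safety Population in both paragraphs, and state that it is the Furoscix cohort of protocol 8.4.
- **Listing:** report eligibility deviations separately, so that a reader can see whether events cluster among those subjects.
- **SAP 3.3.1.3:** the Evaluable Population is nested in the Safety Population and will inherit the change. State whether completing the study phases per protocol is meant to exclude subjects with an eligibility deviation.

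The cost is a few lines of SAP wording and one listing. No extra data are needed, because events are already recorded for everyone dosed. Reported rates could move in either direction.
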